### 13.4 Recording and Evaluation of Adverse Events

The Sponsor expects that all SAEs and selected adverse events highlighted in section 13.3 are recorded from the point of informed consent regardless of whether a patient has yet received a medicinal product. Individual serious adverse events should be evaluated by the investigator, including evaluation of its seriousness, causality and any relationship between the investigational medicinal product(s). The indication for any new concomitant medication, and cause of laboratory abnormality will be captured on the AE CRF page.

#### 13.4.1 Assessment of seriousness

Seriousness is assessed against the criteria in section 13.1.4. This defines whether the event is an adverse event, serious adverse event or a serious adverse reaction.

#### 13.4.2 Assessment of causality

*Definitely:* A causal relationship is clinically/biologically certain. **This is therefore an Adverse Reaction**

*Probable:* A causal relationship is clinically / biologically highly plausible and there is a plausible time sequence between onset of the AE and administration of the investigational medicinal product and there is a reasonable response on withdrawal. **This is therefore an Adverse Reaction.**

*Possible:* A causal relationship is clinically / biologically plausible and there is a plausible time sequence between onset of the AE and administration of the investigational medicinal product. **This is therefore an Adverse Reaction.**

*Unlikely:* A causal relation is improbable and another documented cause of the AE is most plausible. **This is therefore an Adverse Event.**

*Unrelated:* A causal relationship can be definitely excluded and another documented cause of the AE is most plausible. **This is therefore an Adverse Event.**

Unlikely and Unrelated causalities are considered NOT to be trial drug related  
Definitely, Probable and Possible causalities are considered to be trial drug related

A pre-existing condition must not be recorded as an AE or reported as an SAE unless the condition worsens during the trial and meets the criteria for reporting as a SAE or selected adverse event (see section 13.3.)

Investigators will be prompted on the follow up form completed at each visit to complete an infection form or new malignancy form if either of these events have occurred since the last trial visit. Details regarding the changes in dose of IMPs (rituximab, azathioprine, methotrexate and mycophenolate mofetil) including new dose, date of change and reason for change will be captured on the follow up form.

The occurrence of hypogammaglobulinaemia (IgG < 5g/l) is flagged when data is entered into the trial database, and is reported to the DSMB on a 6 monthly basis.

The occurrence of a relevant laboratory abnormality or the addition of a new concomitant medication will be flagged as data is entered into the trial database. An adverse event form will be generated, and the relevant abnormality and data identified pre-filled on the form. Forms will then be sent to investigators for completion. Completed adverse event forms must be submitted to the CCTU within 2 weeks.

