### 9.6 Trial Endpoints

#### 9.6.1 Primary endpoint

The primary endpoint is the time to disease relapse (either minor or major relapse) from randomisation. Any patients who have not relapsed at study close will be censored. Further details of how relapse/censoring dates will be defined are given below.

A blinded Independent Adjudication Committee will be convened to look at all endpoint data.

Situation	Date of Relapse or Censoring	Outcome
No baseline assessments	Randomization	Censored
Relapse documented between scheduled visits	Unscheduled visit date	Relapsed
Drop-out with no relapse	Date of last assessment with no documented relapse	Censored
Treatment discontinuation for undocumented relapse	Date of last assessment with no documented relapse	Censored
Treatment discontinuation for toxicity or other reason, or protocol deviation	The patient will be followed up as per protocol and date of relapse or censoring observed accordingly	Relapsed/censored
Death due to relapse	Date of Death	Relapsed
Death due to other causes	Date of Death	Censored
Death or progression after More than one missed visit	Date of last assessment with no documented relapse	Censored

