### 9.6.2 Secondary endpoints

1. Proportion of patients who maintain remission at 24 and 48 months
2. Time to a major or second minor relapse
3. Cumulative accrual of damage as measured by the combined damage assessment score (CDA)
4. Health-related quality of life as measured using SF-36
5. Cumulative GC exposure
6. Severe adverse event rate
7. Infection (treated with intravenous or oral antibiotics) rates

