#### 13.1.3 **Unexpected adverse reaction**

An adverse reaction, the nature, or severity of which is not consistent with the applicable product information (e.g. investigator's brochure for an unapproved investigational product or summary of product characteristics (SmPC) for an authorised product).

When the outcome of the adverse reaction is not consistent with the applicable product information this adverse reaction should be considered as unexpected.

The term "severe" is often used to describe the intensity (severity) of a specific event. This is not the same as "serious," which is based on patient/event outcome or action criteria.

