#### 13.1.4 **Serious adverse event (SAE) or serious adverse reaction**

Any untoward medical occurrence or effect that:

- Results in death
- Is life-threatening
- Requires hospitalization or prolongs an existing hospitalization
- Results in persistent or significant disability or incapacity
- Is a congenital anomaly or birth defect
- Other important medical events that may not be immediately life-threatening or results in death or hospitalisation but may jeopardise the patient or may require intervention to prevent one of the other outcomes listed in the definition above should also be considered 'serious'

Life-threatening in the definition of a serious adverse event or serious adverse reaction refers to an event in which the subject was at risk of death at the time of event; it does not refer to an event which hypothetically might have caused death if it were more severe.

Important medical events should be reported on the serious adverse event (SAE) form under the 'other' category.

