### **13.5 Reporting Serious Adverse Events**

Each Principal Investigator needs to record all serious adverse events and report these to the Chief Investigators. The Chief Investigators have delegated responsible for assessing all SAEs, to the trial physician, (currently) [name], for expectedness and notification of all SAEs to the Sponsor immediately, but not more than 24 hours after first notification. Individual SAEs will be assessed by the trial physician, and if advice is needed, this will be sought from one of the CIs, blinding them to treatment allocation. The Sponsor has to keep detailed records of all SAEs reported to them by the trial team.

All Serious Adverse Events must be reported to the central trials co-ordinator or trial physician in Cambridge, currently [name] or [name], within 24 hours of the investigator becoming aware of the event, via email ([[contact]](mailto:[contact])). Cumulative safety reports will be generated and sent monthly to the sponsor, the TMC and the DSMB and every three months to all Principal Investigators. All single SAE case reports will also be sent to the DSMB in real-time.

The Chief Investigator is also responsible for prompt reporting of all serious adverse events to the competent authority (e.g. MHRA) of each concerned Member State of findings that could adversely affect the health of subjects, impact on the conduct of the trial or alter the competent authority's authorization to continue the trial in accordance with Directive 2001/20/EC. The Chief Investigator may delegate the responsibility for reporting serious adverse events to the competent authority of any member state outside the UK to the lead investigator for that member state.

An adverse event or reaction that meets serious criteria irrespective of consistency (expected or unexpected) with the applicable product information (e.g. investigators brochure for unapproved investigational product or summary of product characteristics) must be reported to the sponsor unless explicitly listed within the protocol that REPORTING is not necessary.

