## 11 Safety Analyses

### 11.1 Serious Adverse Events

All serious adverse events (SAE), including serious adverse drug reactions will be reported according to guidance in sections 13.4 and 13.5 of the protocol.

All Serious Adverse Events must be reported to the central trials co-ordinator or trial physician in Cambridge within 24 hours of the investigator becoming aware of the event and will be entered in a separate database. Individual SAEs will be assessed by the trial physician, and if advice is needed, this will be sought from one of the CIs, blinding them to treatment allocation. Monthly SAE listings, blinded to treatment allocation, will be reviewed by both CIs however. The Sponsor has to keep detailed records of all SAEs reported to them by the trial team.

Frequency tables for all SAEs will be reported using the safety population and stratified by both treatment arm and induction regimen as well as their interaction.

Separate tables will report:

- SAEs where date of onset occurred after randomisation
- SAEs occurring during treatment (up to 20 months after randomisation)

---

 SAEs occurring during the induction period (prior to randomisation) were reported separately, see Induction Phase SAP and report.

- SAEs occurring after treatment ended (from 20 months after randomisation onwards)

Additionally, counts of subjects and events stratified by relatedness (Unrelated/Related) will be reported, grouped by System Organ Class, High Level Group Term and Preferred Term based on the MedDRA code.

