Figure 29: Forest plot of cox proportional hazards model – Tertiary endpoint.

Figure 30: Serious Adverse Events, forest plot of frequency and relative risk by treatment arm.

Figure 31: Non–serious infections, forest plot of frequency and relative risk by treatment arm.

Figure 32: Kaplan–Meier plot of SAE–free survival by treatment arm.

Figure 33–45: Boxplots by treatment arm of continuous clinical lab tests:  
Haemoglobin, Platelets, WBC, ESR, Creatinine, CRP, ALT, AST, CD19, CD19 (%), IgG, IgM, and IgA.

Figure 46–48: Stacked bar charts by treatment arm of discrete clinical lab tests:  
Anti–PR3, Anti–MPO, and ANCA status.

Figure 49: Alluvial plot of ANCA status by treatment arm, showing change from month 4 to month 24 and to month 36.

Figure 50: Bar charts of EQ–5D–5L questionnaire item's responses.

Figure 51: Boxplot of EQ–5D–5L index totals (VAS Health state, OTT utility score, and VAS utility score) by treatment arm.

Figure 52–54: Bar charts of PROMIS questionnaire item's responses (fatigue, pain, physical ability).

Figure 55: Bar chart of PROMIS questionnaire sub–totals by treatment arm.

Figure 56: Boxplots of PROMIS questionnaire sub–totals by treatment arm.

Figure 57: Boxplot of PROMIS questionnaire total score by treatment arm.

Figure 58–63: Bar charts of SF–36 questionnaire item's responses.

Figure 64: Boxplot of SF–36 questionnaire sub–totals by treatment arm.

Figure 65: Boxplot of SF-36 questionnaire PCS and MCS components by treatment arm.

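### Serious vasculitis relapses count both as primary-endpoint events and as SAEs, and the SAP text plans no overall SAE comparison by arm without them

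*Protocol*

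**What the plan says.** No sentence states outright that a relapse admission is an SAE. It follows from three places in the protocol read together.

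- Section 13.1.4 makes an untoward occurrence serious on outcome criteria, one of which is "Requires hospitalization or prolongs an existing hospitalization". It makes no exception for the disease under study.
- Section 13.4.2 says that a pre-existing condition is not to be "reported as an SAE unless the condition worsens during the trial and meets the criteria for reporting as a SAE or selected adverse event".
- Section 13.5 says that an event meeting a seriousness criterion "must be reported to the sponsor unless explicitly listed within the protocol that REPORTING is not necessary". No relapse exemption is listed. The nearest text, in 13.2 on infusion reactions, skin reactions and low white cell counts, brings reporting back once such an event is serious.

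On efficacy, protocol 9.6.1 states: "The primary endpoint is the time to disease relapse (either minor or major relapse) from randomisation".

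On safety, SAP 11.1 states: "Frequency tables for all SAEs will be reported using the safety population". The tables are split by arm and induction regimen, and cover the whole period after randomisation, the treatment period and the period after treatment. Counts by relatedness and MedDRA level are added. SAP section 13 lists Figure 30, "Serious Adverse Events, forest plot of frequency and relative risk by treatment arm", and Figure 32, a Kaplan–Meier plot of SAE-free survival by arm. The SAP text contains no flag, exclusion or second version for relapse SAEs.

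**The concern.** Long-term safety of rituximab is a secondary objective (protocol 9.5.2), and the trial rationale asks whether sustained rituximab is safe. A reader will look to the overall SAE comparison to weigh harm against benefit. If the drug works, the control arm has more relapses. Some of those lead to admission, and each such admission adds to the control arm's SAE count. The all-SAE comparison then partly repeats the efficacy result. An excess of other SAEs on rituximab could be diluted in the overall frequency, the relative risk and the SAE-free curve, and equal safety could read as a safety advantage.

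**Working it through.** **1. The plan's own figures.** Protocol 16.3 states 58 relapses for 90% power at a hazard ratio of 0.42 and the 5% level (two-sided, SAP 10.1). Schoenfeld's formula gives 4 × (1.960 + 1.282)² / (ln 0.42)² = 55.8, so 56 events; 58 events give 91.0% power. The relapse-free rates of 75% and 50% at 4 years imply a hazard ratio of ln 0.75 / ln 0.50 = 0.415. These figures agree closely enough to use the design rates as inputs.

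**2. Relapsing patients.** With 160 randomised 1:1, there are 80 per arm. Control: 80 × 0.50 = 40. Rituximab: 80 × 0.25 = 20. Dropout is ignored here.

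**3. Relapse SAEs.** Let h be the share of relapsing patients whose relapse is an SAE. The documents do not give it; 10% to 40% is assumed. Patients with a relapse SAE, control v rituximab, are 4 v 2, 8 v 4, 12 v 6 and 16 v 8 at h = 10%, 20%, 30% and 40%. The gap is 2.5, 5.0, 7.5 and 10.0 percentage points.

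**4. Effect on the all-SAE risk ratio.** Let b be the risk of a non-relapse SAE, also not in the documents. If the two sources are independent, P(any SAE) = 1 − (1 − b)(1 − p·h), with p = 0.50 in control and 0.25 on rituximab. Assume b = 30% in control. Two cases follow: b = 36% on rituximab (true ratio 1.20) and b = 30% on rituximab (true ratio 1.00).

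| h | Control | Rituximab, b = 36% | Ratio (true 1.20) | Rituximab, b = 30% | Ratio (true 1.00) |
|---|---|---|---|---|---|
| 10% | 0.335 | 0.376 | 1.12 | 0.3175 | 0.95 |
| 20% | 0.370 | 0.392 | 1.06 | 0.335 | 0.91 |
| 30% | 0.405 | 0.408 | 1.01 | 0.3525 | 0.87 |
| 40% | 0.440 | 0.424 | 0.96 | 0.370 | 0.84 |

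For example, at h = 20% control is 1 − 0.70 × 0.90 = 0.370 and rituximab is 1 − 0.64 × 0.95 = 0.392, a ratio of 1.06.

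The true excess disappears where 0.70(1 − 0.50h) = 0.64(1 − 0.25h). That gives 0.06 = 0.19h, so h is about 32%.

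**5. Sensitivity to independence.** If relapse SAEs fell only on patients who have another SAE anyway, the proportion with any SAE would not move. Positive association between the two sources therefore makes the shift smaller than in the table. Event counts and the timing in Figure 32 could still change.

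**The case against.** The strongest reply is that the harms of most interest have their own outputs, which relapse admissions cannot dilute. Infection rate is a separate secondary endpoint. SAP 11.2 tabulates serious and non-serious infections, counts new IgG below 5 and below 3 g/L, and lists malignancies with treatment arm. SAP 11.4 summarises causes of death, including active vasculitis. SAP 11.1 also breaks SAEs down by relatedness and MedDRA term, and Figure 30 may have term-level rows. This largely stands, and it rules out the inference that the plan would conceal rituximab toxicity.

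It does not supply an overall comparison without relapse SAEs. Relatedness is first judged by investigators in an open-label trial, and that split does not carry over to Figure 32. Relapse may be coded under several organ classes. Figure 31 gives relative risks for non-serious infections only. The full list of tables is in a separate file (SAP section 17) that is not part of the documents, so an unmentioned output cannot be excluded.

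Four further points also stand:

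- **Mainly major relapses.** Protocol 11.6 manages a first minor relapse before month 24 with an oral glucocorticoid increase on continued treatment, so the overlap is mostly with major relapses and h could be low.
- **Deaths.** SAP 10.3 records that all deaths were by other causes, so no fatal relapse is involved.
- **Endpoint wording.** Secondary endpoint 6 reads "Severe adverse event rate". Protocol 13.1.3 separates severity from seriousness, "which is based on patient/event outcome or action criteria". It is an assumption that the SAE analysis delivers this endpoint.
- **Precision.** With 80 per arm, 36% v 30% has an approximate 95% interval for the ratio of 0.77 to 1.87 (standard error of the log ratio √(0.64/28.8 + 0.70/24) = 0.227). The trial could not establish that excess even with relapses removed.

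Finally, a count of all SAEs whatever their cause is a legitimate measure of total burden. A reader might infer that the relapse-excluded count is the true safety comparison. That does not follow: SAEs caused by treatment given after a relapse stay in it, and these would be more frequent in the arm with more relapses.

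**Conclusion.** The concern holds in a limited form. A relapse that meets a seriousness criterion counts on both sides, and the overall SAE comparison and Figure 32 as described do not separate it. The direction is predictable if rituximab works as the design assumes. The size is not known: under the stated assumptions a true ratio of 1.20 reads between 1.12 (10% admitted) and 0.96 (40% admitted), and a true ratio of 1.00 reads between 0.95 and 0.84. These figures rest on the design relapse rates, on assumed admission shares and background SAE risks, and on independence. At the low end the distortion is small. This is an inexpensive improvement to reporting; it does not make the planned safety analysis invalid.

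**What to change.** Leave SAE reporting unchanged, so that relapse admissions remain SAEs. In SAP 11.1 define a flag for an SAE that is a vasculitis relapse. Set it by a prespecified match on subject and date between the SAE database and the adjudicated relapse record in MACRO, with the date window fixed before the analysis. Present the overall SAE frequency and relative risk by arm, and Figure 32, twice: for all SAEs and excluding flagged SAEs. Show both side by side without naming either as the sole safety comparison, and note that SAEs from post-relapse treatment remain in the second version.

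The cost is a match across two databases, one derived variable, a paragraph of SAP text and one extra set of tables and figures. No new data collection or protocol amendment is needed.

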### **13.5 Reporting Serious Adverse Events**

Each Principal Investigator needs to record all serious adverse events and report these to the Chief Investigators. The Chief Investigators have delegated responsible for assessing all SAEs, to the trial physician, (currently) [name], for expectedness and notification of all SAEs to the Sponsor immediately, but not more than 24 hours after first notification. Individual SAEs will be assessed by the trial physician, and if advice is needed, this will be sought from one of the CIs, blinding them to treatment allocation. The Sponsor has to keep detailed records of all SAEs reported to them by the trial team.

All Serious Adverse Events must be reported to the central trials co-ordinator or trial physician in Cambridge, currently [name] or [name], within 24 hours of the investigator becoming aware of the event, via email ([[contact]](mailto:[contact])). Cumulative safety reports will be generated and sent monthly to the sponsor, the TMC and the DSMB and every three months to all Principal Investigators. All single SAE case reports will also be sent to the DSMB in real-time.

The Chief Investigator is also responsible for prompt reporting of all serious adverse events to the competent authority (e.g. MHRA) of each concerned Member State of findings that could adversely affect the health of subjects, impact on the conduct of the trial or alter the competent authority's authorization to continue the trial in accordance with Directive 2001/20/EC. The Chief Investigator may delegate the responsibility for reporting serious adverse events to the competent authority of any member state outside the UK to the lead investigator for that member state.

An adverse event or reaction that meets serious criteria irrespective of consistency (expected or unexpected) with the applicable product information (e.g. investigators brochure for unapproved investigational product or summary of product characteristics) must be reported to the sponsor unless explicitly listed within the protocol that REPORTING is not necessary.

### **13.6 Reporting of Suspected Unexpected Serious Adverse Reactions (SUSARs)**

All suspected adverse reactions related to an investigational medicinal product (the tested IMP and comparators) which occur in the concerned trial, and that are both unexpected and serious (SUSARs) are subject to expedited reporting. Please see section 13.1.6 for the Reference Safety Information to be used in this trial.

#### **13.6.1 Who should report and whom to report to?**

The Sponsor delegates the responsibility of notification of the occurrence of

SUSARs to the Competent Authority (CA), Ethics Committee (EC)/IRB and any other investigators to the Chief Investigators. The Chief Investigators should report all the relevant safety information previously described, to the Sponsor. The Chief Investigators have delegated the responsibility for reporting to the member state Competent Authority and local EC/IRB to the lead investigator of each member state.

The Chief Investigators shall inform all investigators concerned of relevant information about SUSARs that could adversely affect the safety of subjects. Information about SUSARs will be sent to the DSMB within 24 hours of receipt by the Chief Investigators.

### 13.6.2 When and what events to report?

#### 13.6.2.1 Fatal or life-threatening SUSARs

The CA, Research Ethics Committee and Sponsor should be notified as soon as possible but no later than **7 calendar days** after the trial team and Sponsor has first knowledge of the minimum criteria for expedited reporting.

In each case relevant follow-up information should be sought and a report completed as soon as possible. It should be communicated to the CA, Ethics Committee and Sponsor within an additional **8 calendar days**.

In addition to the timelines above, investigators should be aware of, and comply with, the reporting timelines in their respective countries.

